# Regional nodes (N) and distant metastases (M) miN1 miN2 miM1a miM1c miM1b (uni) miM1b (oligo) miM1b (diss) miM1b (dmi)

Figure 5: miTNM categories and pattern of pelvic nodal, distant metastases and bone involvement for reporting prostate cancer stage by F-DCFPyL PET/CT. Tumor involvement is delineated in red. Abbreviations: uni, unifocal; oligo, oligometastatic; diss, disseminated; dmi, diffuse marrow involvement.

In patients with organ involvement (miM1c) all involved organs need to be specified in the final report.

Probability of bone or organ involvement increases with focal uptake, higher PSMA expression score and/or CT/MRI abnormalities. For bone metastases common CT findings include sclerotic, rarely lytic lesions with or without extraosseous extension; common MRI findings include low signal on unenhanced T1 images.

PSMA-positive pitfalls such post-traumatic rib uptake, or non-prostate cancer related primary malignancies have to be ruled out (Rauscher et al., 2016).

# E) Level of Certainty

Reporting level of certainty will be performed as previously proposed by Panicek et al (Panicek and Hricak, 2016) (Table 10).

Term	Numeric estimate
Consistent with	>90%
Suspicious for/Probable/Probably ~75%	
Possible/Possibly ~50%	
Less likely ~25% Unlikely	<10%

# Table 10: Level of certainty.

Certainty will substantially vary depending on uptake, location and CT or MRI findings. For instance at biochemical recurrence certainty of tumor localization will be substantially higher in case of focal uptake at a common location (e.g. internal iliac lymph node) as compared to an uncommon location (e.g. rib).

Standardized wording for level of certainty will improve communication between the reader and the treating physician.

# 1.1.8.3 Treatment Response Assessment

#### 1. miTNM

- a. Any decrease in miTNM class (ex: miT0N2M1b(uni) to miT0N1M1b(uni)) is considered partial response,
- b. Any increase in miTNM class (ex: miTr N1 (IVL) M0 to miT0 N2 M0) is considered progressive disease.
- c. Complete resolution on F-DCFPyL PET is complete response,
- d. No change in miTNM class is stable disease.

#### 2. total PSMA tumor volume

Delineation of total PSMA tumor volume on PET by a yet to be determined algorithm.

- a. Decrease by 30% = PR,
- b. increase by 30% = PD,
- c. Volume = 0 = complete response,
- d. Otherwise stable disease.

#### 1.1.8.4 Measurements

#### 1) Primary Outcome Measurement:

A separate analysis of initial versus subsequent management will be performed.

The principal goal of this study is to evaluate the impact of F-DCFPyL PET/CT on patient management in patients with prostate cancer. The study includes a total of 3 questionnaires; Questionnaires 1 and 2 will be collected from referring physicians prior to and just after completion of the imaging study; these are designed to determine the intended patient management before and intended management changes after PET/CT.

Patients can only be enrolled in the study if the pre-PET questionnaire (Q1) is completed.

*Treatment Modality Analysis*: 3 categories of management changes will be evaluated:

- o no change
- Inter-modality management changes (Major), i.e. change in modality or addition/removal of one or more modalities in the overall management

- Intra-modality management changes (Minor), i.e. same modality before and after PSMA PET/CT, however for instance:
  - Changes in Medical treatment
  - Changes in radiation approach
  - Changes in surgical approach
  - Addition/removal of concomitant ADT

#### Disease stage based management Analysis:

Treatment management will also be categorized as follow: A/ Local Prostate Fossa therapy, B/ Regional Pelvic therapy, C/ Lombo-aortic LN focused therapy, D/ Solitary LN or oligometastatic disease focused therapy and E/ Metastatic disease systemic therapy.

Management change will be classified as: 1/ no change or 2/ change (addition/removal of one or more of these disease stage based treatment strategies)

Questionnaire 3 will be mailed to referring physicians 3-6 months after completion of the imaging study to determine whether intended management changes were implemented.

To assess the implemented treatment management, following methods will be used, in descending priority:

- 1. Systematic electronic chart review when available
- 2. Questionnaire
- 3. Referring physician contact (email, phone or fax)
- 4. Patient contact (email, phone or fax)

#### 2) Secondary Outcome Measurement:

#### A) FOLLOW-UP IMAGING:

All patients will be followed up 3-12 months with conventional imaging (dedicated CT, MRI and/or bone scan). Interpretation of follow-up imaging will be performed by local read. For lesions that are reported in the blinded reads but not reported in the local evaluation of follow-up imaging, the local readers will be informed of the location of the lesions and follow-up will be performed for these additional lesions. Preferably, the follow-up conventional imaging should be the same modality/modalities as the initial staging work-up to allow for reproducible and accurate comparisons.

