#### False positive:

- 1) For patients undergoing systemic treatment (alone or in combination with targeted treatment): If on post-treatment follow-up imaging within 3-12 months, lymph nodes seen on CT or MRI increase by more than 20% in short axis diameter and PSA decreases by more than 50%.
- 2) In subjects with localized suspected lymph node(s) receiving targeted treatment without concomitant systemic treatment there are two ways to meet false positive disease:
  - If the subject does not demonstrate a decrease of PSA by greater than 50% after targeted treatment [OR]
  - If on post-treatment follow-up imaging within 3-12 months, lymph nodes seen on CT or MRI increase by more than 20% in short axis diameter (with a minimum of 3 mm in change in size)
- 3) For untreated patients: If on follow-up imaging within 3-12 months, lymph nodes seen on CT or MRI decrease by more than 30% in short axis diameter (with a minimum of 3 mm in change in size).

If all regions in a patient/region do not meet criteria for either True positive or False positive disease, then the patient/region will be considered unevaluable for primary endpoint.

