#### True positive:

- 1) If there was a corresponding positive sclerotic lesion on the CT portion of the  $^{68}$ Ga- $^{18}$ F-DCFPyL PET or on a separate CT obtained  $\leq$  30 days before or after the PET/CT in the same location as the PSMA uptake.
- 2) If there is focal uptake seen in the same location as the PSMA uptake on the baseline bone scan performed within one month of F-DCFPyL PET.
- 3) If there is a lesion noted in the same location as the PSMA uptake on the initial MRI performed within one month of F-DCFPyL.

- 4) If within 12 months follow-up CT demonstrates development of sclerosis in the same location as the PSMA uptake.
- 5) If within 12 months follow-up MRI demonstrates a new bone lesion in the same location as the PSMA uptake.
- 6) If within 12 months follow-up bone scan demonstrates new focal uptake in the same location as the PSMA uptake.
- 7) In subjects with localized suspected bone lesion(s) receiving targeted treatment without concomitant systemic treatment:
  - If the subject demonstrates a decrease of PSA by greater than 50% after targeted treatment.

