# False positive:

- 1) In subjects with localized suspected bone lesion(s) receiving targeted treatment without concomitant systemic treatment:
  - If the subject does not demonstrate a decrease of PSA by greater than 50% after targeted treatment with curative intent (ie non-palliative radiation).
- 2) If F-DCFPyL positive bone lesions do not meet the criteria for true positive findings, and appropriate correlative and follow-up imaging was acquired.

If bone lesions do not meet criteria for either true positive or false positive disease listed above, then the patient/region will be considered unevaluable for primary endpoint.

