# B) HISTOPATHOLOGY/BIOPSY:

Localization of lesions for histopathology/biopsy will be a classified by regions as specified in the miTNM framework. F-DCFPyL positive findings are aimed to be confirmed by histopathology (HP)/biopsy if clinically feasible. Pathology performed 60 days before the F-DCFPyL PET will be available for correlation. Histopathological procedures, biopsies and follow-up imaging will be performed as clinically indicated and as per institutional protocol.

The following elective procedures may guide the investigator:

Positive HP/Biopsy: Confirmed sites of metastatic or tumor involvement by histopathology/biopsy will be discussed with the responsible physician/surgeon.

- a) *True Positive*: lesion is positive on targeted biopsy/surgical sampling and is read as positive on F-DCFPvL PET.
- b) False Negative: lesion is positive on targeted biopsy/surgical sampling and is read as negative on F-DCFPyL PET.

Negative HP/Biopsy: Patients with suspected tumor recurrence on F-DCFPyL PET with negative histopathology/biopsy will be handled as outlined below:

- 1) Lymph nodes:
  - i) For patients undergoing nodal dissection: Patients will be rescanned with dedicated CT, MRI or a repeat F-DCFPyL PET to determine if the suspicious F-DCFPyL positive node was removed.
    - (1) If F-DCFPyL positive lymph node is still present, a repeat biopsy can be pursued if clinically feasible and applicable, or follow-up using imaging as described above will be performed.
    - (2) If the corresponding node was removed, then this will be considered a False Positive.

- ii) For patients undergoing needle biopsy: Images of the procedure will be reviewed to determine if the correct node was biopsied.
  - (1) If the correct node was biopsied, then a negative biopsy will be considered a False Positive.
  - (2) If the incorrect node was biopsied, then follow-up imaging as described above will be performed.
- 2) Bone lesions: Given the high rate of false negative biopsies for osseous metastases in patients with prostate cancer, patients with negative bone biopsies of PSMA PET positive lesions will be further evaluated:
  - a) If pathology demonstrates an alternative diagnoses that is known to be PSMA positive (eg Renal Cell Carcinoma metastases, Paget's disease), then this will be considered a False Positive.

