# C) DEFINITIONS OF TRUE POSITIVE, FALSE POSITIVE, TRUE NEGATIVE, AND FALSE NEGATIVE PATIENTS AND REGIONS

Pathology will be considered superior to imaging and clinical follow-up when available as described below. Patient and region level classification will be performed for each blinded reader, and be reported separately. The following criteria serve as a guide for interpretation. However not all findings on a lesions, region and patient level can be detailed here and investigators may deviate from these criteria in individual patients. These will be recorded for each interpretation that is not described in this protocol for the definition of a region or patient.

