#### 1) Patient level evaluation:

- a) *True positive patient*: A single region in a patient contains a true positive node either by pathology or imaging/clinical follow-up.
  - i) For a patient to be considered a True Positive, only one region is required to have a true positive lesion as described above, unless one region is categorized as a false positive based on pathology. This means that a single pathology false positive region outweighs regions with imaging/clinical follow-up true positive disease.
  - ii) A patient will be considered a True Positive if one region contains a lesion that is True Positive, even if other regions are categorized as inevaluable or false positive based on imaging or clinical follow-up.

- b) *True negative patient*: in the absence of True Positive or False Positive lesions, a patient will be considered a True Negative if there is pathology that is negative for disease and corresponding lesion is negative by F-DCFPyL PET.
- c) False positive patient:
  - i) Pathology confirms a false positive lesion that is read as positive on F-DCFPyL PET.
  - ii) In the absence of pathology: there are no true positive regions, and there is a region that is categorized as false positive based on imaging or clinical follow-up.
- d) False negative patient: in the absence of True Positive or False Positive lesions, a patient will be considered a False Negative if there is pathology that is positive for disease and corresponding lesion is negative by F-DCFPyL PET.
- 2) Region level evaluation: Each patient will have four evaluable regions (Table 1: prostate bed, pelvis, extrapelvic soft tissue, and bone metastases). Each region will be categorized as true positive or false positive as described above. Regions without evidence of F-DCFPyL positive disease or deemed unevaluable will not be included in the analysis.
  - a) True positive region:
    - i) Pathology confirms a F-DCFPyL avid lesion as a true positive in the region. ii) In the absence of pathology, clinical or imaging follow-up demonstrates a true positive lesion within the region independent of the presence of an inevaluable lesion or a false positive lesion (ie true positive disease will supersede a false positive lesion in the region based analysis if based on imaging/clinical follow-up).

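### The follow-up imaging rule is stated two ways, and PPV is calculated on evaluable PET positives without counting the regions lost or bounding their effect

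*Combined protocol and SAP*

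**What the plan says.** - **Who is imaged.** Section 1.1.8.4, 2) A) Follow-up imaging: "All patients will be followed up 3-12 months with conventional imaging (dedicated CT, MRI and/or bone scan". Section 1.1.8.4, 2) B) Histopathology/Biopsy: "Histopathological procedures, biopsies and follow-up imaging will be performed as clinically indicated and as per institutional protocol".
- **What happens to unclassified positives.** The lymph node and visceral rules end by saying that patients or regions which "do not meet criteria for either True positive or False positive disease, then the patient/region will be considered unevaluable for primary endpoint". The bone and prostate rules end in similar words. Under C), region level evaluation, regions without "positive disease or deemed unevaluable will not be included in the analysis". At patient level one true-positive region suffices, "even if other regions are categorized as inevaluable or false positive based on imaging or clinical follow-up".
- **Room for judgement.** Under C), pathology outranks imaging and clinical follow-up, and "investigators may deviate from these criteria in individual patients", with such cases recorded.
- **Bone.** One of three baseline routes to a true positive reads "If there is focal uptake seen in the same location as the PSMA uptake on the baseline bone scan performed within one month of"; the other two use CT and MRI. The default false positive applies when "positive bone lesions do not meet the criteria for true positive findings, and appropriate correlative and follow-up imaging was acquired".
- **Analysis.** Section 1.1.9.5 plans PPV per patient and per region with Wilson 95% intervals for each of three blinded readers, plus a per-patient detection rate by PSA stratum that does not depend on verification. Section 1.1.9.2 analyses endpoints in the whole cohort and in the initial and subsequent groups. The primary endpoint (1.1.3.3) is management change; PPV is secondary.

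**The concern.** The follow-up rule decides which PET-positive lesions receive a reference standard. With two statements of it, staff could image everyone or only those with a clinical reason, and both could claim to follow the protocol. Positives left unverified then drop out of the PPV. The Wilson interval describes sampling error among those that remain and says nothing about those that left. No count of excluded regions, no breakdown by reason and no bounds are planned.

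Two details add to this. The unevaluable sentences refer to the primary endpoint, although the rules they close serve the secondary PPV; read literally, they would remove patients from the management-change analysis. And the bone rules treat the two outcomes unequally, so missing follow-up does not remove true and false positives in equal proportion.

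**Working it through.** The documents give no expected PPV, number of positives or unevaluable share, so there is no plan figure to reproduce here. The only design calculation (1.1.9.6) concerns management change.

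**1. Can the loss be reconstructed?** At patient level, largely: for each reader, unevaluable positives = detection-rate numerator − (TP + FP). The gap is PSA below 0.2 ng/mL, which has no stratum, although response-assessment patients (1.1.4) have no PSA floor. At region level, no: detection rate is per patient only, and the categories under C) are TP, FP, TN and FN.

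**2. Is loss foreseeable?** 400 patients (1.1.3.1) at 100 a year (1.1.9.7) take 48 months, and study completion is month 48 (1.1.3.4). With even accrual, if follow-up stops there:
- under 3 months of follow-up: 400 × 3/48 = 25 patients (6.25%);
- under 12 months: 400 × 12/48 = 100 patients (25%).

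If all 400 are enrolled by month 36 (133 a year), both figures are zero. Imaged lesions can also stay unclassified. An untreated 10 mm node needs 13 mm or more for TP (over 20% and at least 3 mm growth) and under 7 mm for FP (over 30% and at least 3 mm shrinkage). Between these it meets neither rule, unless pathology, another lesion or a recorded deviation settles the region.

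**3. What the interval omits.** With observed PPV p and unevaluable share u, the bounds are p(1−u), all unevaluable counted as false, and p(1−u)+u, all counted as true. Their width is u whatever p is. Illustration with 300 positives and p = 90%, both assumed:

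| u | TP/evaluable | Wilson 95% | Bounds |
|---|---|---|---|
| 10% | 243/270 | 85.8–93.0% | 81–91% |
| 30% | 189/210 | 85.2–93.4% | 63–93% |
| 50% | 135/150 | 84.2–93.8% | 45–95% |

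The interval hardly moves while the bounds widen from 10 to 50 points. At u = 6.25% and p = 90% the bounds are 84.4–90.6%.

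**4. Bone.** Let π be the share of positive lesions that are truly metastatic (assumed 0.7–0.9), a the share of true lesions with a baseline correlate (0.3–0.7), b the share of false lesions with one (0–0.2), and f the share with follow-up imaging, taken as unrelated to truth. PSA and pathology rules are set aside, and true lesions without a baseline correlate are assumed to show one later.

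- T = π[a + (1−a)f] + (1−π)b
- F = (1−π)(1−b)f
- PPV = T/(T+F)

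F shrinks in proportion to f. T does not, because its baseline part stays. So PPV rises as f falls.

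Example with π = 0.8, a = 0.5, b = 0:
- f = 1: 0.800/1.000 = 80.0%
- f = 0.9375: 0.775/0.9625 = 80.5%
- f = 0.75: 0.700/0.850 = 82.4%

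Over the whole grid, the change against f = 1 is +0.2 to +0.9 points at f = 0.9375 and +0.7 to +4.2 points at f = 0.75.

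Complete follow-up does not remove all bias. At f = 1, PPV = π + (1−π)b. With π = 0.7 and b = 0.2 this is 0.76 against a true 0.70. Over the grid the baseline-correlate rule itself adds 0 to +6 points.

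**The case against.** **The two imaging statements can be reconciled.** The all-patients sentence stands under its own follow-up heading. The other is in the histopathology section, just before guidance described as elective, and can be read as leaving modality and timing to the clinic. A reader might infer a flat contradiction; the text does not establish one. What stands is that the limit is not written down.

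**The timeline proves little.** The accrual rate is a planning figure, and nothing says follow-up of late enrollees ends at month 48. A reader might take 25% as the expected unevaluable share. The documents do not support that: the window opens at month 3, bone lesions can be confirmed at baseline, and pathology or PSA rules can classify without later imaging. The 25% is an extreme.

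**Part is already covered.** Patient-level loss is largely derivable, deviations are recorded, and PPV among evaluable positives is a legitimate quantity for a descriptive secondary endpoint with no threshold. This limits the weight of the point but does not supply the missing region-level counts.

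**The bone direction is not absolute.** True lesions that never acquire a correlate become false positives when follow-up is complete, which pushes PPV down. The upward tendency is therefore relative to complete follow-up, not to the truth. A reader might also infer that complete follow-up would leave bone PPV unbiased; step 4 of the working shows otherwise.

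**Conclusion.** The point holds as a weakness in the definition and reporting of the secondary PPV endpoint. The follow-up rule is ambiguous, unevaluable regions are dropped, their number cannot be recovered from the planned output, and the Wilson interval does not reflect the loss. For bone, incomplete follow-up tends to raise PPV against complete follow-up by the amounts in step 4, and the baseline rule can add to this independently. Those figures rest on assumed inputs and on follow-up being unrelated to lesion truth; across all regions the bias could go either way, and its actual size cannot be derived from the documents. Lesion gaps also do not pass one-for-one to patients, since one true-positive region can classify the patient.

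A reader might infer from the unevaluable sentences that the management-change result is at risk. That endpoint is measured by questionnaires and chart review, and once the wording is corrected it is unaffected. The change should be made; confidence is medium.

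**What to change.** 1. State one follow-up rule in 1.1.8.4 A) and B). If follow-up is declared clinical, no extra scans are needed. Say whether follow-up of the last enrolled patients continues past month 48.
2. In the lymph node, visceral, bone and prostate rules, replace the reference to the primary endpoint with PPV.
3. In 1.1.9.5, report for each reader the number of unevaluable PET-positive patients and regions, split into imaged but indeterminate and not followed up.
4. Beside the evaluable-only PPV, show the bounds with all unevaluable positives counted as false and then as true, labelled as bounds, at least for the patient and bone rows.
5. Give the number of bone true positives that rest on baseline imaging alone.

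Cost: wording and table rows. Three readers × three populations × five rows (patient plus four regions) gives 45 PPVs and up to 90 bound figures. Limiting bounds to the patient and bone rows gives 3 × 3 × 2 × 2 = 36. All are arithmetic on the same counts. The downside is a wider, less favourable reported range.

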# 1.1.9.4 Prognostic Value Analysis:

Clinical outcome is defined by:

- Radiographic PFS: time from inclusion to date until first site of disease is found to progress or death (whichever occurs first)
- Nodal and visceral disease is evaluated on cross-sectional imaging using RECIST 1.1/PCWG3 criteria
- b) Bone metastases are evaluated using bone scintigraphy and new lesions have to be confirmed on a second scan (2+2 rule) using PCWG3 criteria
  - Biochemical PFS: time from inclusion to date until PSA progression or death (whichever occurs first) (Scher et al., 2016)
- a) for patients with PSA decline: Time from baseline to time the PSA increase to 25% and 2 ng/ml above nadir which is confirmed by a second value ≥3 weeks later
- b) for patients without PSA decline: Time from baseline to time the PSA increase to 25% and 2 ng/ml above baseline
  - Overall survival: Time from inclusion to date of death.

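### Local readers are told where the PET-positive lesions missing from their follow-up read lie, and no unprompted read is kept; for bone this may raise the PPV by an amount that cannot later be measured

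*Combined protocol and SAP*

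**What the plan says.** Section 1.1.8.4, Secondary Outcome Measurement, part A (Follow-up imaging) sets the reading procedure: "Interpretation of follow-up imaging will be performed by local read". It then adds an exception. "For lesions that are reported in the blinded reads but not reported in the local evaluation of follow-up imaging", the plan says, "the local readers will be informed of the location of the lesions and follow-up will be performed for these additional lesions". It has no matching rule for sites that are PET-negative. It does not require the local read to be fixed before disclosure, and it plans no analysis that leaves out prompted findings.

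For bone, three of the true-positive criteria rest on follow-up imaging:
- item 4: "If within 12 months follow-up CT demonstrates development of sclerosis in the same location as the PSMA uptake"
- item 5: a 12-month window in which "follow-up MRI demonstrates a new bone lesion in the same location as the PSMA uptake"
- item 6: "If within 12 months follow-up bone scan demonstrates new focal uptake in the same location as the PSMA uptake"

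None of the three has a size threshold or needs a PSA change. Under the bone False positive heading, item 2, lesions are false positive if they "do not meet the criteria for true positive findings, and appropriate correlative and follow-up imaging was acquired". Bone lesions that meet neither definition are unevaluable.

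Part C (Definitions) ranks pathology above imaging. Within a region, a true positive on imaging overrides a false positive on imaging. One true-positive region makes the patient true positive, unless pathology has shown a false positive. Section 1.1.9.5 reports PPV per patient and per region, with Wilson intervals, for each of three blinded readers.

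**The concern.** Where there is no pathology, follow-up CT, MRI and bone scan are the standard against which the PET is judged. The exception lets the PET result steer that standard. It acts only where PET is positive and the local read is silent, and it tells the reader where to look. Prompting is sensible when a node has to be found in order to be measured. A call of present or absent is more open to suggestion, and the bone criteria are calls of that kind.

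The quantity at stake is the bone-region PPV and, through the patient-level rule, the per-patient PPV. Both belong to the second secondary endpoint. If the prompted read replaces the unprompted one, nobody can later say how much of the reported PPV came from prompting.

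**Working it through.** The documents give no expected bone PPV and no rate of prompted changes, so there is no planned figure to reproduce. The sample-size statement in section 1.1.9.6 concerns management change, which this rule does not touch.

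**Step 1: which way a prompted look can move a bone lesion**

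| Status before the prompt | Possible status after it | Effect on PPV |
|---|---|---|
| True positive by baseline CT, bone scan or MRI (items 1–3) or PSA response (item 7) | unchanged | none |
| Settled by pathology | unchanged | none |
| False positive by default, imaging already adequate | false positive, or true positive by items 4–6 | none or up |
| Unevaluable, if the added follow-up supplies the missing imaging | true positive or false positive | up or down |

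The one-way effect is confined to the third row. In nodes, visceral lesions and the prostate, class depends on size and PSA change, so a prompted measurement can go either way.

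**Step 2: formula for the third row**

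Let T be the regions confirmed unprompted, F the default false positives, and q the share of F changed by prompting.

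Reported PPV = (T + qF)/(T + F) = PPV + q(1 − PPV), which cannot fall as q rises.

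**Step 3: illustration limited to regions decided by follow-up imaging (assumed T = 20, F = 20)**

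- q = 0: 20/40 = 50%
- q = 10%: (20 + 2)/40 = 55%
- q = 30%: (20 + 6)/40 = 65%
- q = 50%: (20 + 10)/40 = 75%

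**Step 4: the same, adding 40 regions already confirmed by unexposed routes (also assumed)**

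- q = 0: 60/80 = 75%
- q = 10%: 62/80 = 77.5%
- q = 50%: 70/80 = 87.5%

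The largest shift falls from 25 to 12.5 percentage points.

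**Step 5: a scale tied loosely to the documents**

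The abstract at the front of the document reports skeletal metastasis on PET in 7 of 41 patients. Scaled to the planned 400, 7/41 × 400 ≈ 68 patients, taken here as 68 evaluable bone regions. I assume that every false positive is of the default kind and round changes to whole regions.

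| Unprompted PPV (95% Wilson) | q = 10% | q = 50% (95% Wilson) |
|---|---|---|
| 41/68 = 60% (48.4–71.1%) | 44/68 = 65% | 55/68 = 81% (70.0–88.5%) |
| 61/68 = 90% (80.2–94.9%) | 62/68 = 91% | 65/68 = 96% (87.8–98.5%) |

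The effect is large only if many lesions are default false positives and prompting changes many of them. The same abstract has mpMRI positive for bone in 1 of 41. That suggests PET-positive sites unreported on conventional imaging may be common, but it is a baseline comparison and not follow-up data.

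**Step 6: from region to patient**

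A changed bone region turns a false-positive patient into a true-positive one only if no other region is already true positive and no pathology false positive exists. A region or patient with another imaging true positive does not move.

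**The case against.** The best defence is that a lesion left out of a local report is not a lesion looked for and found absent. A local reader may simply not mention a faint finding, and a directed look may put that right. On this view the unprompted PPV is the one at fault, since it counts omissions as PET errors. This stands in part: the documents cannot show what share of changed calls would be mistakes. It argues for keeping both reads, not for discarding one.

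A second defence is that added follow-up can make an unevaluable bone lesion evaluable as a false positive, which lowers PPV. That also stands. The one-way argument holds only where imaging was already adequate.

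Two stronger readings are tempting, and the documents support neither.
- A reader might infer that a blinded reference read is being unblinded. The plan never says that local readers are masked to the PET. The bone criteria themselves require findings to be matched to the site of uptake. The defect is that no read made before disclosure is preserved.
- A reader might infer that prompting creates radiographic progression in PET-positive patients and so inflates the prognostic value of miTNM. Section 1.1.9.4 defines that endpoint as "time from inclusion to date until first site of disease is found to progress or death (whichever occurs first"), names no reader and makes no reference to the prompting rule. It judges bone by scintigraphy with confirmation on a second scan, so newly noticed CT sclerosis or an MRI bone lesion would not count as bone progression. Nor is it shown that patients with more PET disease would be prompted more often, since extensive disease may be reported without help.

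**Conclusion.** The point holds for bone-region PPV and for the per-patient PPV that follows from it. For lesions without decisive pathology and with adequate follow-up imaging, prompting can only raise the PPV. The reference standard then depends partly on the test it is meant to judge. Whether the rise is bias or correction cannot be known unless the unprompted read is kept, so the PPV may be biased upward; the documents do not prove that it is.

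The size is not derivable from the documents. The range of 5 to 25 points in Step 3 rests on an assumed 50% unprompted PPV, on change rates of 10% to 50%, and on counting only regions decided by follow-up imaging. Mixing in regions settled by baseline imaging, PSA response or pathology reduces it. The primary endpoint on management change is unaffected, and no conclusion about radiographic PFS is drawn.

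**What to change.** Amend the Follow-up imaging paragraph of section 1.1.8.4, and add one line to section 1.1.9.5:

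1. The local reader records and locks the follow-up read before any PET location is disclosed for that read.
2. The prompted re-read goes into a separate field. It may be used to locate and measure nodal and soft-tissue lesions under the size rules.
3. For bone true-positive items 4–6, bone-region PPV and the resulting per-patient PPV are reported both without and with prompted confirmations.

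The lock does not make the local read blinded; it makes the contribution of prompting visible. It should not be extended to restrict radiographic PFS to unprompted findings, because that could discard real progression.

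The cost is one extra data field and additional table rows: 3 readers × 2 staging groups × 2 levels (bone region, patient) = 12 further estimates, or 18 if the whole cohort is shown as a third group. The re-read is already planned, so sample size and power do not change and no further scans are needed. The unprompted PPV will tend to look less favourable and may count some missed lesions as false positives, which is why both figures should appear.
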